Study start-up is anticipated to take approximately 12 months. This time period will be used to finalize the protocol, study documents, case report forms, and electronic data capture system; to form and hold the initial meeting of the DSMC and ensure all study personnel are trained in study procedures. The IND for the study was cleared by the FDA on July 7, 2016. The local IRB has previously approved the study protocol and informed consent form. Any changes to the study protocol and informed consent form recommended by the DSMC will be submitted to the FDA and local regulatory agencies (IRB and Stem Cell Oversight Committee) for final approval before study enrollment begins. The UC Davis Eye Center (Enrollment Center) clinical trial team has been involved in many multi-center clinical trials funded by NEI and has an excellent track record. In addition, the Enrollment Center is involved in the on-going phase I study of this cellular therapy. Thus, the team is experienced in all aspects of this proposed study except the randomized treatment assignment, sham-control design, and masking procedures.

The DCC (Emmes) has contributed to the study design and the Manual of Procedures prior to study start-up. There has been continuous communication between the DCC and the Study Chair/PI and this communication will continue through study start-up and through the duration of the study.

Study Recruitment (approximately 42 months):

Recruitment is anticipated to take the 42 months. Note the FDA had initially mandated that enrollment be staggered by at least two weeks in the event that there is a safety issue observed associated with the study therapy. Although this mandate has been lifted recently in the cross-referenced IND based on available safety data of the pilot study, a conservative rate of enrollment is advised and planned. For the early part of enrollment for this phase I/II study (i.e., first 6 months of the enrollment period starting from the date the study was open to enrollment), enrollment will be staggered by at least 2 weeks.

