An additional factor affecting rate of enrollment is the limited number of days the treatment can be administered. Available treatment days will be limited since the participant, the hematologist, the GMP facility, and the study treating ophthalmologist must all be available concurrently for study treatment to be administered. Furthermore, enrollment is anticipated to be slower than expected due to travel restrictions imposed by the COVID-19 pandemic that began during the study enrollment.

During the recruitment period, a biannual update on study enrollment and study retention rate will be presented to the DSMC by the DCC. Any study-related safety issues will also be presented. In addition, the Study Chair/PI will communicate at least monthly with the DCC regarding the recruitment schedule and study progress.

Study Follow-up (approximately 12 months):

Following the end of the study recruitment period, an additional 12 months will be required to allow all participants to complete the study. During this period, all efforts will be made by the masked investigators and Study Coordinator at the Enrollment Center to avoid early study dropout. Because participants remain masked to therapy assignment during the follow-up, it is anticipated that there will be minimal dropout during the first six months until all participants receive the second study therapy. At that point, all participants will have received the cellular therapy, and more likely that participants may consider dropping out of the study. The Enrollment Center team will make every effort to encourage the study participants to keep all follow-up study visits to ensure participants are adequately followed for safety following this experimental therapy and so that the study can gain information regarding the effects of the cellular therapy, whether they be potentially beneficial or adverse.

Study Closeout (approximately 6 months):

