Ophthalmic History	х	х	х	х	х	х	х	х	х	х	х	х	х	
Assessment of Concomitant Medications	х	x	х	х	х	x	х	x	x	x	х	х	х	х
Informed Consent	х													
Vital Signs	х	X#	х	х			х	X#	х	х				
CBC	х			х			х			х				
Urine Pregnancy Test**	х						х							
ETDRS VA	Х	X^	X	X	х	х	х	X^	X^	X	х	х	х	
Micro-Perimetry	х				х	х	x				х	Х	х	
Eye Exam & IOP	х	X@	х	х	х	х	x	X@	x	х	х	х	х	
Fundus Photography	х					х	x					х	х	

TABLE 2: Study Visit Schedule														
	Screening Period	Study Period 1						Study Period 2					Study Exit^^	
Visit	Screening/ Baseline 1	Study Treatment 1	Day 1	Week 1	Month 1	Month 3	Month 6/ Baseline 2 *	Study Treatment 2 *	Day 1	Week 1	Month 1	Month 3	Month 6	
Target Month	+	-	-	-	1	3	6	-	-	-	7	9	12	**
Target Day	-	0	1	7	28	91	181	182	183	190	210	273	364	**
Window	+	-	-	±2 d	±7 d	±14 d	±30 d	±30 d	-	±2 d	±7 d	±14 d	±30 d	**
FA	х					х	х					х	х	
OCT/OCTA	х				х	х	х				х	х	х	
Inclusion/ Exclusion Criteria	х													
Randomization	х													
AF	Х					х	Х					Х	х	
ERG***	Х				х	х	Х				Х	Х	Х	
NEI VFQ	Х						Х						Х	
Advanced retinal imaging ^{@@}	х				х						х			
Hematology Consult	х						х							
Cellular or Sham Therapy ^{##}		х						x						
Adverse Events	Х	Х	Х	Х	х	х	Х	Х	Х	Х	Х	Х	Х	Х
Enrollment Pause Guideline Review			х	х	Х	х	x	х	x	x	x	х	х	

TABLE 2: Study Visit Schedule														
	Screening Period		Study Period 2					Study Exit^^						
Visit	Screening/ Baseline 1	Study Treatment 1	Day 1	Week 1	Month 1	Month 3	Month 6/ Baseline 2 *	Study Treatment 2 *	Day 1	Week 1	Month 1	Month 3	Month 6	
Target Month	+	-	-	-	1	3	6	-	-	-	7	9	12	**
Target Day	-	0	1	7	28	91	181	182	183	190	210	273	364	۸۸
Window	+	-	-	±2 d	±7 d	±14 d	±30 d	±30 d	-	±2 d	±7 d	±14 d	±30 d	۸۸
Post Procedure Satisfaction Survey				х						х				
Study Satisfaction Survey													х	х

Abbreviations: AF—fundus autofluorescence; CBC—complete blood count; FA—fluorescein angiography; IOP—intraocular pressure; OCT/OCTA—optical coherence tomography and angiography; VA—visual acuity; ROS—review of systems.

Shaded cells represent visits which are conducted by unmasked staff.

*Screening assessments may be done in one or more visits within 1 month of study treatment at Day 0 although results from within 45 days prior to study treatment at Day 0 may be considered at the discretion of the investigator.

*The Baseline 2 visit and the Study Treatment 2 visit must be separated by at least one day but no more than 30 days.

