Once the participant qualifies for the study, the participant will be randomized 1:1 to either of the following study treatments: immediate cell therapy/deferred sham therapy or immediate sham therapy/deferred cellular therapy, where cell therapy consists of bone marrow aspiration and intravitreal injection of isolated CD34+ cells and sham therapy consists of sham bone marrow aspiration and sham injection. Immediate therapy refers to procedure administered at baseline while deferred therapy refers to procedure administered at month 6 of the study. The following assessments will be completed prior to study treatment that occurs on Day 0 and may be performed before or after randomization depending on the clinic or participant scheduling needs: autofluorescence, full field and multifocal electroretinography (ERG) and quality of life questionnaire. Additional imaging using a research-grade ultra-high-resolution OCT/OCTA and adaptive optics-OCT instruments will also be performed on a select subgroup of participants who qualify and consent.

Prior to randomization, the participant will meet with the study hematologist to review the aspiration procedure. The hematologist will review the participant's medical history, concomitant medications and blood work (including CBC) to ensure that the participant is a good candidate for a bone marrow aspiration. Any abnormal lab work and review of systems will be reviewed by the hematologist to determine whether it would impact the outcome of the bone marrow aspiration procedure and continued enrollment in the study.

Using the DCC's electronic data capture (EDC) system, Advantage eClinical[®], the unmasked Study Coordinator will randomize the participant, and will disseminate this information in a confidential manner to the hematologist and GMP laboratory as described in section 6.1.2.

On the morning of the study procedure, the participant will meet with the hematologist and the unmasked study coordinator to ensure there are no new contraindications to proceeding with study treatment that day.

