The participants will have a complete eye examination 1 day and 1 week (±2 days) after their first study treatment (either cell or sham) by the unmasked treating ophthalmologist. Thereafter, a follow-up examination 1 month (±7 days), 3 months (±14 days) and 6 months (±30 days) will be conducted by the masked examining ophthalmologist. At month 6, the participant will receive the second study treatment (either cellular or sham therapy which is the opposite of what they originally received) by the unmasked treating ophthalmologist. Prior to the receipt of the second study treatment, the participant will meet with the study hematologist to review the aspiration procedure. Similar to the first consult, the hematologist will review the participant's medical history, concomitant medications, and blood work (including CBC) to ensure that the participant is still a good candidate for bone marrow aspiration. Any abnormal lab work and review of systems will be reviewed by the hematologist to determine whether it would impact the outcome of the bone marrow aspiration procedure and continued treatment in the study. In addition, females of child-bearing potential must have a negative pregnancy test within 2 weeks of the second study treatment. Similar to what occurs for the first treatment, the study team will meet with the participant on the morning of the study procedure to ensure there are no new contraindications to proceeding with study treatment that day.

Following the study injection, the unmasked treating ophthalmologist will conduct a follow-up exam 1 day and 1 week after this second study treatment. The masked examining ophthalmologist will conduct an exam 1 month, 3 months (\pm 14 days) and 6 months (\pm 30 days) after the second study treatment (i.e., at approximately 7, 9 and 12 months after the first study treatment).

The bone marrow aspiration wound site will be inspected visually for infection at the 1 day and 1 week (±2 days) post-procedure examinations by the unmasked treating ophthalmologist.

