
The study is a randomized prospective study in which participants and all study personnel participating in eye examinations and outcome assessment will remain masked for the study duration of 12 months. Only the advanced retinal imaging team, treating ophthalmologist, the hematologist conducting bone marrow aspiration, and the study coordinator conducting these treatment and immediate post-treatment examination visits will be unmasked. All participants will remain masked for the study duration. The study design allows all participants to receive cellular therapy by month 6. The rationale for this study design is based on the expectation that participants receiving intravitreal cell injection would likely note a beneficial effect of cellular therapy, if any, by month 3 based on the observations of the preliminary phase I study.²²

The proposed clinical trial is supported by preclinical observations. Human CD34+ cells from bone marrow have been shown to be multi-potent and observed to home into ischemic retinal blood vessels and damaged retinal cells very quickly following intravitreal injection in animal models.¹⁵⁻¹⁹ These human cells could be detected in mouse retinal vasculature as long as 6 months following intravitreal injection in a murine model of acute retinal ischemia-reperfusion with apparent normalization of the retinal vasculature.¹⁷ No long-term safety issues were noted locally or systemically in the murine study. Of note, the number of CD34+ cells injected into the murine eyes in these preclinical safety studies is equivalent to about 10 million CD34+ cells injected in human eyes if adjusted for differences in eye size and volume. Thus, the upper limit of number of viable nucleated CD34+ cells to be injected intravitreal for this phase I/II study will be 10 million, where the cell count is based on the Miltenyi CliniMACS cell sorting process.

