In addition, the following pause guidelines have been established. If any of the following events occur, enrollment will be paused, and the data reviewed by the DSMC.

- 1. Development of any new intraocular tumor in the injected eye during the study period in any participant.
- Endophthalmitis or Severe Inflammation resulting in > 3 lines of vision loss attributable to the study therapy in any participant, i.e., final culture of cell isolate shows organism despite negative immediate release tests, or this AE is noted in two or more participants despite negative final culture and immediate release tests.
- 3. Loss of vision of > 3 lines not attributed to normal progression of the eye condition, noted in two or more participants during the study period. The DSMC will be notified at the time that one participant has loss of vision of > 3 lines, but a pause would not be triggered until a second participant experiences the event.
- 4. New retinal vascular event in the study eye during the study period noted in two or more participants not attributable to normal progression of the underlying eye condition during the study period.
- Development of ocular neovascularization in the study eye not attributable to normal progression of the underlying eye condition during the study period in two or more participants.
- 6. Development of new sustained elevation in intraocular pressure above 30 mmHg not controlled with medical therapy and/or paracentesis and directly attributed to the studied therapy in any participant.

7. Any adverse event leading to enucleation or loss of the eye directly related to study therapy.

These guidelines may be further refined by the DSMC before initiation of the study. In the event any of these pause guidelines are triggered during the course of the study, both the IRB and FDA will be notified within 7 days and the study enrollment will be paused until further notice from the FDA and/or IRB. The study participant will be followed and treated according to standard of care until condition stabilizes or resolves.

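### A triggered pause guideline automatically stops enrollment only; it does not hold Treatment 2, when the deferred arm receives its first cell injection

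*Protocol*

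**What the plan says.** Protocol 6.4 sets out seven events that trigger a pause. The response is stated before the list, "If any of the following events occur, enrollment will be paused, and the data reviewed by the DSMC", and again after it: the IRB and FDA are told within 7 days and "the study enrollment will be paused until further notice from the FDA and/or IRB". The affected participant is followed and treated under standard of care. Nothing is said about treatments still due in other participants.

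The matching row in Table 2 (Protocol 6.1.5) is labelled "Enrollment Pause Guideline Review". It is marked at every visit from Day 1 to Month 12, including Study Treatment 2.

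On timing, Protocol 6.2 says: "The study design allows all participants to receive cellular therapy by month 6". Table 2 places Treatment 2 at day 182 ±30. Protocol 6.1.4 gives the calendar: "Recruitment is anticipated to take the 42 months", and then "Following the end of the study recruitment period, an additional 12 months will be required to allow all participants to complete the study".

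**The concern.** In a trial with one treatment per participant, stopping enrollment largely stops exposure. Here every participant is meant to receive cells, and half of them do so months after joining. Several triggers point to harm from the product itself: an intraocular tumor, an organism grown from the cell isolate, or loss of the eye. If the rule is followed as written, someone already enrolled may have a first cell injection while such an event is under review, unless a responsible body steps in. Some of these exposures could be avoided altogether; others would only be postponed if the review cleared the product.

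The rule also loses its automatic effect at the end of the trial. Once recruitment closes there is no enrollment left to pause, but deferred cell injections go on for about 5 to 7 months.

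**Working it through.** **Text.** The two statements of the response in 6.4 agree with each other and with the Table 2 label: all three name enrollment. Protocol 6.1.5 uses different words for the hematologist's two reviews. Before Treatment 1 the question is the effect on the "bone marrow aspiration procedure and continued enrollment in the study"; before Treatment 2 it is the effect on the "bone marrow aspiration procedure and continued treatment in the study". The eligibility criteria (7.1.2.1) equate enrollment with the date of consent, whereas the first of those two phrases applies it to someone who has already consented. So it is unclear whether a pause covers a consented participant awaiting Treatment 1. For Treatment 2, the natural reading is that it is not covered.

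**Inputs.**
- 20 participants, randomized 1:1 (Protocol 3.0 and 7.8.3).
- Recruitment of 42 months (Protocol 6.1.4).
- Treatment 2 at day 182 ±30, so days 152 to 212 (Table 2).
- Notice to IRB and FDA within 7 days (Protocol 6.4).
- Assumptions: even accrual, an even split of arms, and 30.44 days per month. Accrual of 30 and 54 months is used as a range.

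The documents give no figure for pending injections, so there is none to reproduce.

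**Whole-trial total.** 20 × 1/2 = 10 deferred cell injections, half of the 20 planned.

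**Rate.** 10 / 42 = 0.238 deferred cell injections per month.

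**Participants awaiting deferred cells at a given time** = rate × gap between treatments.
- Day 152: 152 / 30.44 = 4.99 months; × 0.238 = 1.19
- Day 182: 5.98 months; × 0.238 = 1.42
- Day 212: 6.96 months; × 0.238 = 1.66
- At day 182 the figure is 1.99 for 30-month accrual and 1.11 for 54-month accrual.

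**Deferred cell injections in the 7-day notice period, given a trigger.**
- 7 / 30.44 = 0.230 months; expected number 0.238 × 0.230 = 0.055
- Chance of at least one: 1 − exp(−0.055) = 0.053, about 5%
- 30-month accrual: expected 0.077, chance 7%. 54-month accrual: expected 0.043, chance 4%.

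**Deferred injections after the last Treatment 1.** Under even accrual this equals the number awaiting at that moment: 1.19, 1.42 or 1.66 of 10, that is 12%, 14% or 17%.

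**The case against.** The strongest reply is that a trigger does much more than pause enrollment. It also requires DSMC data review and notice to the IRB and FDA, whether or not enrollment is open, and 7 days is the outer limit for that notice. The DSMC is told of the first qualifying vision loss, before the two-participant threshold is met (6.4). SAEs reach the coordinating center within 24 hours (8.6), and the Medical Monitor informs the DSMC after confirming them (6.4). The DSMC can recommend modification, and several bodies can stop the study at any time (7.7). Early stopping is discussed with the DSMC before the trial begins, alongside pausing of enrollment (6.1.6). Treatment 2 needs several teams available together (6.1.4), and contraindications are rechecked that morning (6.1.5). The pilot reported no safety issues.

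This stands as a reason to expect that a hold would usually follow. It does not supply the rule: each step is either left to judgment or, like the morning check, concerns that participant's own fitness rather than a signal from the trial.

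A second reply is that the triggers for vision loss, new vascular events and neovascularization are not confined to cell-treated eyes, so events after sham alone could suspend all treatment. That is true, but the protocol already accepts an automatic pause for all seven triggers without that distinction.

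Third, the word enrollment is used loosely, and the pause review is marked at Treatment 2, so a wider meaning may have been intended. If so, the text should say it.

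Finally, the DSMC charter and Manual of Procedures are not among the documents, and the DSMC could refine the guidelines before the study began. A hold may already exist there.

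**Conclusion.** The gap is real and worth closing, but it is modest. The only automatic restriction on treatment is a pause of enrollment, and pending treatments are held only if someone decides to hold them. Confidence is medium because of the unseen charter and manual.

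A reader might infer that 10 cell injections are at risk whenever a guideline is triggered. The documents do not support that: 10 is the total over the whole trial, and about 1.2 to 1.7 participants await deferred cells at any one time. Nor do they support the inference that a trigger after recruitment closes has no consequence, since DSMC review and regulatory notice still apply.

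All figures are conditional on a trigger and rest on even accrual; no unconditional risk can be derived. The 5% covers the notice period only. The pause itself is open-ended, but longer exposure would require that no informed body acted, so it is not quantified.

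**What to change.** In both sentences of Protocol 6.4, replace the pause of enrollment with a pause of *enrollment and all pending Treatment 1 and Treatment 2 procedures, cellular and sham*, lasting until the DSMC has reviewed the data and the FDA and/or IRB give notice to resume. State that it also applies after enrollment closes. Sham procedures must be held too, because holding only cell procedures would reveal the assignment.

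To avoid contradictions elsewhere, add *unless a safety hold is in effect* to:
- the sentences in Protocol 6.1 and SAP 3.1 that tie the second treatment to within a month of the 6-month visit;
- the Treatment 2 window in Table 2;
- the Table 2 footnote limiting the gap between Baseline 2 and Treatment 2 to 30 days.

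After a hold, repeat Baseline 2 if it is more than 30 days old and use the repeat as the Period 2 baseline (SAP 4.2.2). Keep the original Month 6 data as the 6-month outcome, and count Period 2 visits from the actual Treatment 2 date. The existing pregnancy-test and anti-VEGF spacing rules already apply and need no new text.

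The cost is one protocol amendment, agreed with the DSMC, FDA and IRB, plus small edits to SAP 3.1 and 4.2.2. Some Treatment 2 visits would be delayed and some Baseline 2 tests repeated. Study Period 1, the primary safety window, would be longer for held participants, so the length of each hold should be listed beside the Period 1 adverse events. In the immediate-cell arm, a held participant's last visit would fall later than 12 months after the cells, which the 12-month analysis should note.

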6.5 Compliance with Laws and Regulations

This study will be conducted in accordance with current U.S. Food and Drug Administration (FDA) Good Clinical Practices (GCP), and the Institutional Review Board and Stem Cell Oversight Committee of the University of California Davis Medical Center.

7.0 MATERIALS AND METHODS

7.1 Participants

7.1.1 Participant Selection

All participants will be enrolled at the Retina Clinic at the University of California Davis Eye Center. The participants may include patients already being treated in the clinic and patients referred to the Enrollment Center for consideration for study enrollment. All patients with persistent vision loss from CRVO will be considered for enrollment if they meet the eligibility criteria.

7.1.2 Inclusion/Exclusion Criteria

7.1.2.1 Study Eye Inclusion/Exclusion Criteria

Inclusion criteria for the study eye are:

- 1. Clinical diagnosis of central retinal vein occlusion (CRVO) confirmed by review of medical records and screening assessment.
- 2. BCVA obtained during the screening period is in the range of 20/40+ to 20/400- (ETDRS letter score in the range of 18 to 73, inclusive).
- 3. Duration of vision loss from CRVO \geq 6 months to \leq 42 months.

Exclusion criteria for the study eye are:

- 1. Previous eye treatment with intravitreal or periocular steroids, laser or intraocular surgery within 6 months prior to enrollment (i.e., date ICF signed) or treatment is expected to be given during the study period.
- For eyes requiring treatment to prevent recurrent macular edema, on-going intravitreal anti-VEGF treatment is expected to be given at an interval < every 8 weeks during the study period or anti-VEGF therapy was started less than 24 weeks prior to informed consent.
- 3. History or concurrent ocular herpes infection.
- 4. Active non-herpetic eye infection diagnosed within 8 weeks from enrollment (i.e., date ICF signed).
- 5. Glaucoma requiring treatment with more than 2 medications, laser or intraocular surgery.
- 6. Active uveitis or history of recurrent uveitis or uveitis involving the posterior segment.
- 7. Presence of cataract that is impairing vision.
- 8. Presence of lens or lens implant subluxation.
- 9. History of ocular trauma that is currently impairing vision.
- 10. Any concurrent optic nerve or retinal disease that is visually significant or likely to progress to visual significance during the 1-year study follow-up. The excluded eyes include eyes with AREDS category 2 to 3 age-related macular degeneration (AMD) with foveal involvement of drusen or RPE changes, and any AREDS category 4 AMD eyes. For eyes with ERM, the excluded eyes include eyes with OCT evidence of foveal deformation. For optic nerve disease, eyes with any associated visual field deficit or history of associated

CNVM are excluded. For glaucoma eyes, eyes requiring glaucoma laser trabeculectomy or glaucoma surgery to maintain IOP are excluded.

- 11. Active retinal or iris neovascularization.
- 12. Macular edema requiring on-going therapy or where such treatment is expected during the study period, with the exception of anti-VEGF treatment given at an interval of 8 weeks or greater.
- 13. Significant media opacity precluding view of the fundus for examination, photography or optical coherence tomography (OCT) including cataract and vitreous haze.
- 14. High myopia (\geq 9 diopters)
- 15. Amblyopia
- 16. Other cause contributing to vision loss at screening.
- 17. History of any of the following procedures: corneal transplant, glaucoma surgery, or intraocular silicone oil.

